This is a randomized control, open-label, single-site clinical trial. We will target completion by eighty adolescents (age 12-17 years) with Type 1 diabetes and their parent/guardian (age 18+) to participate in a 3 month outpatient study. Participants will be randomized to either a Control Group or Experimental Group. Both groups will use the study continuous glucose monitor, study activity tracker, and a study insulin pen if an multiple daily injection (MDI) user. Subjects who use an insulin pump to treat their type 1 diabetes will use their personal insulin pump. All subjects will be asked to download this equipment and provide it to the study team each week. The study team will communicate weekly with each group. Questionnaires will also be completed at the beginning and at the end of the study. The Experimental Group will receive the CloudConnect Reports. The Control Group will not receive this feedback.

3. Does the study involve a placebo?

No

Human Participants

Ages: 12-17 years old and at least one of parent(s)/guardian(s) (age 18+)/guardian (adolescent/parent dyad is required for participation in this trial)

Sex: Male and Female

Race: All

1. Provide target # of subjects (at all sites) needed to complete protocol.

For the Pilot Study, up to 6 adolescents and 6 parent(s)/guardian(s) may complete the study. These pilot subjects may also participate in the Main Study.

For the Main Study, 160 subjects (80 dyads – consisting of 80 adolescents and 80 adults) need to complete the study.

2. Describe expected rate of screen failure/ dropouts/withdrawals from all sites.

We expect that because the length of the study it could be 20-30% dropouts/withdrawals from the study.

3. How many subjects will be enrolled at all sites?

This is a single site clinical trial to be completed at UVa.

4. How many subjects will sign a consent form under this UVa protocol?

Up to 210 subjects (105 dyads – consisting of 105 adolescents and 105 parent(s)/guardian(s)) will sign consent for the Main Study and up to 16 subjects (8 parent/child dyads) will sign a consent for the Pilot Study. i.e. total = 226 (210+16)

Inclusion/Exclusion Criteria

1. List the criteria for inclusion for Pilot and Main Study Adolescent Subjects

- Willingness to provide informed consent
- Adolescents ages ≥ 12 and ≤ 17 years old with a parent/guardian (18+ yo) who is willing to participate with the child

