Use of anti-diabetic agents other than short-acting insulin for CSII subjects or long-acting insulin for MDI subjects, including: metformin, sulfonylureas, meglitinides, thiazolidinediones, dipeptidyl peptidase 4 (DPP-4) inhibitors, glucagon-like peptide 1 agonists and alpha-glucosidase inhibitors

Statistical Considerations

1. Is stratification/randomization involved? Yes

► IF YES, describe the stratification/ randomization scheme.

During the main study, up to 210 adolescents, ages 12 years - 17 years (inclusive), will be recruited with one of their parent(s)/guardian(s), 18+ y.o., in each arm. Based on experience, approximately 40 adolescents & 40 parent(s)/guardian(s) in each arm will complete the study (N=80 adolescents and 80 parents, total 160 subjects). Male and female adolescents will be recruited, and all racial/ethnic groups will be eligible for participation. Participants will be recruited in randomization blocks of 4. The goal is to target a minimum of 10 participants in each of the 4 stratification subgroups based on age (12-14 y.o and 15-17 y.o.) and insulin therapy (CSII and insulin pen). ,

► IF YES, who will generate the randomization scheme?

Sponsor
 UVa Statistician. Answer/Response:
 UVa Investigational Drug Service (IDS)
 Other: Center for Diabetes Technology (CDT) personnel

2. What are the statistical considerations for the protocol?

The objectives section and the statistical section should correspond, and any objective for which analysis is unfeasible should be deleted. Also, the estimates and non-statistical assumptions of the statistical section should be supported by discussion in the background section.

The answer to this question should include:

-Study Design/Endpoints

- Recap of study objectives and endpoint definitions. An assessment of how study objectives will be assessed by identifying & defining which endpoints will be used to assess each component of the study objectives.
- The study design should include contingencies for early stopping, interim analyses, stratification factors (If applicable), and any characteristics to be incorporated in analyses.
- The power/precision of the study to address the major study endpoint(s), the assumptions involved in the determination of power/precision.

Study Design:

This study employs a randomized design in which one group of participants will be assigned to use the CloudConnect system and the other group to CGM using their insulin paramenters and treatments.

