Study Objectives & Endpoint Definitions:

As mentioned previously, this project seeks to assess how CloudConnect affects participant engagement, dyad engagement, and clinical outcomes in adolescent T1D.

We will assess how adolescents and their parent(s)/guardian(s) respond to this new approach using the Family Communication Inventory (FCI). This diabetes-specific approach was designed by the investigators to assess parent-child communication regarding tasks (discussion of insulin dosing for a given meal, BG trends, need for dose changes). As an outcome measure, scores for parents and adolescents are summed, with higher scores representing higher degree of engagement and T1D-specific communication.

Power/Precision of the study to address major study endpoints:

In using the FCI, we determined based on preliminary data from 220 adolescent/parent participants eligible for the study, with mean (90.3) and standard deviation (12.5) that we are powered to detect a difference of 8.5% in this outcome in the treatment group with 80% power and an alpha of 0.05. This study will require 40 adolescent participants with 40 parent(s)/guardian(s) to complete per arm. Assuming a non-adherence/drop-out rate of 20-30% for Intention-to-Treat (ITT) analysis, 55 participants is yielded per arm.

3. Provide a justification for the sample size used in this protocol.

The study team will attempt to enroll an equal number subjects based on gender, CSII, and MDI use. The study is powered to detect a difference of 8.5% in this outcome in the treatment group with 80% power and an alpha of 0.05. This study will require 40 adolescent participants with 40 parent(s)/guardian(s) to complete per arm. Assuming a non-adherence/drop-out rate of 20-30% for Intention-to-Treat (ITT) analysis, 55 participants is yielded per arm.

4. What is your plan for primary variable analysis?

Because this is a randomized study, our primary outcome (score on the Family Communication Inventory) will be by t-test comparing those randomized to CloudConnect to usual care+CGM. Comparison of secondary outcomes between treatment groups will also be t-tests. Secondary analyses of both the primary and secondary outcomes will utilize multivariable ANOVA, particularly in the event that key variables differ between groups. For example, if average steps per day [as a measure of exercise] is higher in one group vs.

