another, this will be used as a variable in the comparison of mean glucose by CGM to evaluate whether there remained a difference in mean glucose once total daily steps was taken into account. Similarly, if there is an imbalance of key participant characteristics among participants who complete the study in one treatment group (such as higher proportion of multiple-daily-injection participants in the CloudConnect group), this will be considered as a variable in the multivariable ANOVA comparing mean glucose by CGM, as a secondary analysis.

5. What is your plan for secondary variable analysis?

- HbA1c
- Mean glucose by CGM
- Percent time in range 70-180 mg/dL
- Percent time in range 70-150 mg/dL
- Percent time <70 mg/dL
- Percent time >180 mg/dL
- Number of low BG
- Average daily insulin dose
- Average grams of carbohydrate entered
- Steps/day by Fitbit
- Questionnaires: Family Conflict Scale, Division of Diabetes Responsibilities, Child Self Management and My-Q scores.
- Response to weekly standardized questions:
 - i. *During the past week, did you talk with your parents about your diabetes management?*
(Yes=1, No=2)
 - ii. If you answered “yes,” how good or bad was the tone of that conversation?
(Likert scale: Very good = 1; good =2; Neutral = 3 bad =4; Very bad =5)
 - iii. During the past week, did you change your insulin parameters?
(Yes=1, No=2)

6. Have you been working with a statistician in designing this protocol?

No

7. Will data from multiple sites be combined during analysis?

No

Study Procedures-Biomedical Research

1. What will be done in this protocol?

PILOT STUDY:

Up to six adolescent subjects and six parent(s)/guardian(s) will be enrolled in a Pilot Study to assess the components used by the Experimental Group of the Main Study. This trial will evaluate if: (i) subjects can be trained to use study CGM + study Fitbit + personal pump (if pump user) or study insulin pen for mealtime

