Both groups will participate in the same number of visits (completed either in clinic or via phone or video conferencing) and follow up communication contacts done by phone calls, text messages and/or emails during the entire length of the trial. The production of the CloudConnect Report, in combination with the available Dexcom alarms and apps, is the study differential between groups.

*Secondary health outcomes: Average Blood Glucose values by Continuous Glucose Monitor; average total daily insulin; average carbohydrate of grams entered; number of insulin boluses; average number of steps by day

Figure 1: Study Design

There are four visits in the Main Study. Visit 1 and 2 may be combined and may be in person or via phone or video conference. A repeat Hemoglobin A1c will be collected if visit 1 and 2 are greater than 28 days. Visit 3 may be completed by phone. In addition, there will be weekly communication done by phone call, text message and/or email throughout the entire 12 weeks (3 months) of the data collection portion of the study. Method of weekly communications with the adolescent and parent will be based on participant/parent preference. The study team will communicate separately with the child and the parent in order to obtain their feedback independent of the other.

Subjects will be asked to electronically complete the following questionnaires at the completion of Visit 1 and repeated again at the conclusion of their study participation. Questionnaires may be answered remotely (i.e. at home) within a week of the visit or during a CRU visit.

- Blood Glucose Monitoring Communication questionnaire (Hood et al Diab Care 2004)
- Child and Parental Responsibility Questionnaire (adapted from Anderson et al J. Ped Psychol 1990)
- Child Self-Management
- Diabetes Care and Communication
- Diabetes Family Conflict Scale-Revised (Hood et al Diab Care 2007)
- Family Communication Inventory

- MY-Q (deWit et al Ped Diab 2012)
- Questions about CloudConnect use (CloudConnect group only, asked only at study end):
 - On a scale of 1-7, with 1 being very difficult and 7 being very easy, how easy was it to understand the information provided in the weekly reports? Can you tell me why you gave the score you did? What could have made the weekly reports easier to understand?

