 - On a scale of 1-7, with 1 being not at all useful and 7 being very useful, how useful were the weekly reports in helping you communicate with your parents/child about managing your/your child's diabetes? Can you tell me why you gave the score you did? What could have made the weekly reports more useful to you?
 - Is there anything else you would like to tell us about your experience with the weekly reports?

The weekly contact by phone, email or text for both the Control and Experimental Groups will be to:

- Check for AE or SAE
- Remind to download all the data (i.e. CGM, insulin pump/insulin pen, Fitbit data)
- Ask standardized questions, which will include the following:
 - For the child participant:
 - During the past week, did you talk with your parents about your diabetes management?
Yes or No
 - If you answered "yes," how good or bad was the tone of that conversation?
(Likert scale: Very good good Neutral bad Very bad)
 - During the past week, did you change your insulin parameters?
(Yes=1, No=2)
 - For the adult participant:
 - During the past week, did you talk with your child about his/her diabetes management?
Yes or No
 - If you answered "yes," how good or bad was the tone of that conversation?
(Likert scale: Very good good Neutral bad Very bad)
 - During the past week, did your child change his/her insulin parameters?
(Yes=1, No=2)

(Yes=1, No=2)

Visit 1: Adolescent subjects will be screened as indicated in the inclusion/exclusion criteria, and the consent form will be signed electronically after all the question related to the study are answered. The consenting process may occur over the phone/video or in-person. Demographic information and medical history information will then be obtained. A physical exam can either be performed at Visit 1 or documentation of a physical exam at a physician/provider visit within one year will suffice. Hemoglobin A1c will be collected with point-of-care equipment or at a local laboratory. This can be omitted if it is not possible to go to a laboratory or come to the clinic because of governmental restrictions such as Stay-at-Home orders. A urine pregnancy test will be required for adolescent girls who are able to become pregnant. Test must be negative to participate in the study.

If the adolescent subject meets eligibility, visit 1 and 2 may be combined. A repeat Hemoglobin A1c will be collected if visit 1 and 2 are greater than 28 days.

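### Average daily insulin dose is compared with no allowance for body size in 12-17 year-olds, which costs precision on a secondary outcome but does not bias it

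*Combined protocol and SAP*

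**What the plan says.** All references are to the combined protocol and SAP.

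- **The outcome.** Statistical Considerations, item 5, lists "Average daily insulin dose" as a secondary variable. The note on secondary health outcomes at Figure 1 (Study Procedures, Main Study) calls it "average total daily insulin". Neither place gives a unit or mentions body size.
- **The test.** Item 4 of the same section: "Comparison of secondary outcomes between treatment groups will also be t-tests".
- **The adjusted analysis.** Item 4 continues: "Secondary analyses of both the primary and secondary outcomes will utilize multivariable ANOVA, particularly in the event that key variables differ between groups". Its two worked examples are daily steps and the share of multiple-daily-injection (MDI) users, both for mean glucose.
- **The population.** Inclusion criteria: "Adolescents ages ≥ 12 and ≤ 17 years old", of both sexes.
- **The randomization.** Item 1 describes blocks of 4 and "4 stratification subgroups based on age (12-14 y.o and 15-17 y.o.) and insulin therapy (CSII and insulin pen").
- **A possible source of weight.** Visit 1 includes a physical exam, but "documentation of a physical exam at a physician/provider visit within one year will suffice". Weight, height and BMI are not named anywhere as a measurement, covariate or stratification factor.
- **The size of the comparison.** "This study will require 40 adolescent participants with 40 parent(s)/guardian(s) to complete per arm".

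**The concern.** Insulin requirement broadly rises with body size, and body size varies a good deal between ages 12 and 17 and between the sexes. The weekly report may change how insulin is used, but it cannot change how large the participant is. When daily dose is compared by a plain t-test, the part of its spread that follows size counts as noise.

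The existing safeguards do not remove that noise. Stratifying by age band limits imbalance in size between arms, but a t-test that ignores the strata leaves the age-related variance in its standard error. Size also varies within each band, and sex is not a stratification factor. The multivariable ANOVA is aimed mainly at observed imbalance, not precision, and no body-size variable is named for it.

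At stake is a wider confidence interval and lower power for one secondary outcome. Leaving the scale unstated also leaves the choice of scale open until the data are in.

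**Working it through.** **1. The plan's own figure.** The only power statement concerns the FCI: mean 90.3, SD 12.5, difference 8.5%, 80% power, alpha 0.05. The difference is 0.085 × 90.3 = 7.68 points. The normal approximation, two-sided, gives n = 2 × (1.960 + 0.842)² × 12.5² / 7.68² ≈ 42 per arm, and 78.4% power at 40 per arm. That is close to the stated 40 and 80%. It says nothing about insulin dose, for which the documents give no mean, SD, effect size or power.

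**2. Assumptions for an illustration.** None of these is in the documents.
- units/day = weight × units/kg/day, both lognormal
- CV of weight (c_w): 15-25%
- CV of units/kg/day (c_u): 25-30%
- correlation between the two: zero at first

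**3. Formulas.**
- CV(units/day) = √(c_w² + c_u² + c_w²c_u²)
- Share of relative variance removed by scaling = 1 − c_u² / CV(units/day)²
- Detectable difference at 40 per arm, two-sided 0.05, 80% power = (1.960 + 0.842) × √(2/40) = 0.626 SD (0.634 by the exact t-test)

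**4. Results with no correlation.** The two detectable differences are percentages of the mean. The last column takes an effect that would have 80% power in units/kg/day.

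| c_w | c_u | CV(units/day) | Variance removed | Detectable, units/day | Detectable, units/kg/day | Power in units/day |
|---|---|---|---|---|---|---|
| 15% | 25% | 29.4% | 28% | 18.4% | 15.7% | 66% |
| 15% | 30% | 33.8% | 21% | 21.2% | 18.8% | 70% |
| 20% | 30% | 36.6% | 33% | 22.9% | 18.8% | 63% |
| 25% | 25% | 35.9% | 52% | 22.5% | 15.7% | 50% |
| 25% | 30% | 39.8% | 43% | 24.9% | 18.8% | 56% |

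In the middle row, units/day would need 60 per arm to match what 40 per arm gives in units/kg/day.

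**5. Results if units/kg falls as weight rises.** On the log scale, v = s_w² + s_u² + 2ρs_w s_u with s² = ln(1 + c²), and CV(units/day)² = exp(v) − 1. For c_w = 20%, c_u = 30%, ρ = −0.3: v = 0.0392 + 0.0862 − 0.0349 = 0.0905, so CV² = 0.0947. Against c_u² = 0.09 the variance ratio is 1.05, and scaling removes only about 5%. For the other four rows, in table order, the ratio is 1.00, 0.95, 1.42 and 1.21. The effect of scaling therefore runs from removing about 30% of the variance to adding about 5%.

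**6. What this does not measure.** The table is for scaling by an accurate current weight. The gain from adjusting for age, sex and insulin therapy cannot be computed from the documents.

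**The case against.** The strongest reply has four parts.

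- **The label is silent.** Neither mention of the outcome says units/day or rules out units/kg/day. This stands: the plan is under-specified, not shown to have rejected scaling. But taken as written, a daily dose or daily total is an unscaled quantity.
- **The plan already has tools.** Randomization is stratified by age band and therapy. The ANOVA covers secondary outcomes, and its wording does not strictly confine it to imbalance. This stands in part. Age, sex or therapy could enter under that provision, but nothing commits the team to it for insulin dose, and the stated prompt is imbalance.
- **The size of the loss comes from outside the documents.** This stands in full. With a modest negative correlation the loss can vanish.
- **A weight may not exist.** This also stands. Visits may be by phone or video, an exam up to a year old is accepted, and weight is not listed. Dividing by an outdated weight in a growing adolescent adds error of its own.

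A reader might infer that differences in dose largely reflect body size. The illustration does not support this: the share removed exceeds half only near one corner of the assumed range and is as low as 21% elsewhere, before any negative correlation. A reader might also infer that a chance imbalance in size would pass for a treatment effect. In a randomized comparison the test's alpha already allows for chance imbalance.

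**Conclusion.** The point holds as a modest loss of precision. Insulin dose is listed without scaling, compared without adjustment, and measured in adolescents whose size varies, so variance that could be explained is left in the error term. Under the assumed CVs with no correlation, the detectable difference at 40 per arm is about 18-25% of the mean unscaled, against 16-19% scaled, and scaling removes 21-52% of the variance. With a correlation of −0.3 the benefit is smaller and in places absent. Every figure here rests on those assumptions.

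The documents do not support saying that the plan biases the comparison or hides a dosing effect. No particular effect on dose is hypothesized, and the expected consequence is a wider interval. The outcome is one unpowered item in a long secondary list, so this is an optional improvement.

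**What to change.** **Change.** Add to Statistical Considerations, item 5, before outcome data are examined:

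1. The unit of average daily insulin dose.
2. That the arms are compared by a linear model adjusted for age, sex and insulin therapy (CSII or MDI), whatever imbalance is observed. These are known from the demographic data and the stratification, so nothing new is collected.
3. That where a weight is available from the Visit 1 exam or the accepted exam record, it is added as a covariate or the outcome is also reported in units/kg/day. State in advance which of the two. The covariate form is safer if dose does not rise in proportion to weight.

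**Cost.** A sentence or two in the plan and, for the third item, one field taken from the exam record.

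**Limits.** Weight is not named as collected and may be missing or up to a year old. That is why the model in item 2 should be the main comparison. A weight taken from an exam before randomization cannot be affected by the assigned arm, so its age adds noise rather than a systematic difference between arms. The change also leaves a separate gap. The study pen is supplied for mealtime boluses, and no source is stated for long-acting insulin in MDI users, so their daily total may be incomplete. The therapy covariate can absorb a difference in level between CSII and MDI users, but it cannot recover insulin that was never recorded. The plan should say what the daily total contains.

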Using this approach, it is expected to address the informatics challenge of determining how to design information technology that improves engagement and clinical outcomes for patients who require continuous monitoring and who engage an informal caregiver in self-management outside clinical settings. Our work extends the design of remote-monitoring systems from stationary, home-based systems to wearable devices that patients can engage with throughout an active day in the community. Our research team—which consists in a biomedical systems engineer, a human factors engineer specialized in consumer health informatics, a pediatric endocrinologist, and a pediatrician specialized in clinical research — works in alliance with the Center for Diabetes Technology at the University of Virginia. Study team members have developed this ambulatory platform that will be used as the foundation for this study.

Rationale: The hypothesis of this study is that individuals randomized to the CGM/Fitbit with no weekly feedback (Control Group) will improve management modestly initially (as a result of either of new access to CGM or the Hawthorne effect of being studied), but their measures of engagement (patient self-management behavior (i.e. personal insulin parameters) and diabetes-related dyad communication) will return to baseline levels by the 12-week evaluation. By contrast, it is hypothesize that individuals randomized to CloudConnect (Experimental Group) will have a greater increase in engagement and dyad communication by 8 weeks that is sustained by 12 weeks (3 months).

It is further hypothesize that adolescents randomized to CloudConnect will have a lowering of HbA1c that is related to the increase in dyad disease-specific engagement. Moreover, our hypotheses are that this unique self-management approach in T1D will increase engagement of adolescents and their informal caregiver through increased communication and self-management behavior, and that this increase in engagement will lead to improved medical outcomes.

These hypotheses are based on data from preliminary studies collected by the study group and the literature. This preliminary data support that parents of adolescents with T1D are eager to follow their child's blood

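### Weekly tone is scored only in weeks when the respondent talked, and CloudConnect aims to increase talking, so the planned tone t-test is not a comparison of randomised groups

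*Combined protocol and SAP*

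**What the plan says.** Statistical Considerations, item 5, lists three weekly questions among the secondary outcomes. The first is the gate: "During the past week, did you talk with your parents about your diabetes management". The second applies only after a yes and asks "how good or bad was the tone of that conversation", coded as "Likert scale: Very good = 1; good =2; Neutral = 3 bad =4; Very bad =5", so a higher score is worse. A week answered no has neither a tone score nor a code. Item 5 gives the child's wording; the Main Study weekly contact in Study Procedures puts the same gated pair to the parent separately.

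On analysis, item 4 says: "Comparison of secondary outcomes between treatment groups will also be t-tests". It makes no exception for tone. Multivariable ANOVA is a secondary analysis for imbalances and does not address the gate. The contacts run "throughout the entire 12 weeks (3 months) of the data collection portion of the study", but no rule says how a respondent's weekly answers are combined.

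The Rationale under Objectives/Hypothesis expects measures of engagement, including dyad communication, in the Control Group "will return to baseline levels by the 12-week evaluation". It expects a larger rise with CloudConnect by week 8, sustained to week 12. The intervention is meant to raise engagement "through increased communication and self-management behavior".

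**The concern.** Whether a week yields a tone score is decided after randomisation, by a behaviour that the intervention is designed to change. If CloudConnect leads dyads to talk in weeks when they would otherwise have been silent, those extra weeks enter the Experimental Group's tone average and have no counterpart in the Control Group. The t-test then mixes two things: any change in how conversations go, and a change in which conversations are scored. A between-arm difference in mean tone could appear with no change in the conversations that would have happened anyway, and a real change could be hidden or exaggerated. What is at stake is the reading of one secondary outcome.

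**Working it through.** The plan states no expected value, effect size or power for tone, so there is no figure to reproduce. The documents supply the gate, the 1-5 scale, the t-test, 12 weeks and 40 completing dyads per arm. Talk rates and tone distributions are **assumptions**.

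**1. Share of good tone among talk weeks.** Let pc and pt be the shares of weeks with talk in Control and Experimental, u the share of usual conversations with good tone, and a the share among added ones. Usual conversations are taken as unchanged by treatment.

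- Control: u
- Experimental: [pc·u + (pt − pc)·a] / pt
- Difference: (a − u)(pt − pc) / pt

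With u = 70% and a = 40%:

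| Talk, Control v Experimental | Experimental, good tone among talk weeks | Difference from 70% |
|---|---|---|
| 60% v 80% | (0.60×0.70 + 0.20×0.40)/0.80 = 62.5% | −7.5 points |
| 80% v 90% | (0.80×0.70 + 0.10×0.40)/0.90 = 66.7% | −3.3 points |
| 90% v 95% | (0.90×0.70 + 0.05×0.40)/0.95 = 68.4% | −1.6 points |

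The difference is zero if a = u or pt = pc, and positive if a > u.

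**2. Mean score on the 1-5 scale.** Let b be the true effect on the tone score of a conversation (negative is better), and g how much higher (worse) added conversations score than usual ones. The expected observed difference is b + g(pt − pc)/pt. At 60% v 90% talk:

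- b = 0, g = 1.0: 1.0×0.30/0.90 = +0.33, looks worse.
- b = 0, g = −0.5: −0.5×0.30/0.90 = −0.17, flatters CloudConnect.
- b = −0.2, g = 1.0: −0.20 + 0.33 = +0.13, the sign is reversed.

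For b = −0.2 the sign reverses only if g > 0.2·pt/(pt − pc). That is 0.2×0.90/0.30 = 0.6 at 60% v 90%, and 0.2×0.90/0.10 = 1.8 at 80% v 90%, a very large gap on a five-point scale.

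**3. The 60% v 80% illustration over all weeks.**

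| Week type | Control | Experimental | Change |
|---|---|---|---|
| Talked, good tone | 0.60×0.70 = 42% | 42% + 0.20×0.40 = 50% | +8 points |
| Talked, not good | 0.60×0.30 = 18% | 18% + 0.20×0.60 = 30% | +12 points |
| No talk | 40% | 20% | −20 points |

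Good-tone weeks rise, and so do weeks with a conversation not rated good.

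**4. What the good-tone share measures.** If talk rises from 60% to 80% and tone stays at 70% good, the share moves from 42% to 0.80×0.70 = 56%: a gain of 14 points with no change in tone. It cannot stand alone as a tone outcome.

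**5. Simulation.** This used 4,000 trials per scenario, 40 dyads per arm and 12 weeks, with assumed mean tone 2.2, between-dyad SD 0.6 and within-dyad SD 0.8, and talk at 60% v 90%.

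- b = −0.2, g = 1.0: mean tone among talkers differed by +0.13 and was significantly worse with CloudConnect in about 16% of trials. Good-tone weeks rose by 13.7 points and bad-tone weeks by 7.4.
- b = 0, g = 0: tone among talkers differed by essentially zero, yet good-tone weeks rose by 18.6 points.

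The first result shows why tone among talkers can mislead; the second shows why the good-tone share must be read with talk frequency.

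**The case against.** Several points on the other side are sound.

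- **The gate may barely move.** The question asks about any talk in a whole week, whereas the hypothesis concerns communication in general. More talk within a week that is already a yes week leaves the gate unchanged. If most dyads talk weekly, little selection remains, as the 90% v 95% row shows. This stands, and it limits the size.
- **Talking is already a separate secondary outcome.** Reading talk frequency beside tone is a reasonable two-part description. This helps a careful reader, but the plan does not link the two items, and the tone t-test still conditions on talking.
- **Other measures have no gate.** The Family Conflict Scale is a listed secondary outcome, and the Main Study also collects a Blood Glucose Monitoring Communication questionnaire at baseline and study end. Family interaction therefore does not rest on tone alone, though these measures do not repair the tone test.

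A reader might also infer that the plan will make a beneficial report look harmful. The documents do not support that. They give neither talk rates nor the tone of added conversations, and the bias can equally favour CloudConnect. In the 60% v 80% illustration, conversations not rated good rise by more (12 points) than good ones (8 points). The average conversation there really is less good, so calling the scenario a benefit is a value judgement.

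**Conclusion.** The structural point holds on the documents alone: tone is gated on talking, talking is what the intervention aims to change, and the tone comparison is a t-test with no stated handling of no-talk weeks. Direction and size are not established. Under the assumed 70% and 40% good-tone shares, the apparent difference runs from −7.5 points (60% v 80% talk) to −1.6 (90% v 95%); with better-toned added conversations it changes sign. There is no bias if talk rates are equal, or if added conversations have the same tone as usual ones. The FCI comparison and its sample size are not touched. This is a low-priority, cheap improvement that can be settled before analysis.

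**What to change.** For each respondent separately (the child as listed in item 5, with the parent reported alongside), classify every answered week as one of four states: no talk; talked with good or very good tone; talked with neutral tone; talked with bad or very bad tone. Present all four by arm.

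Compare the arms on the shares of good-tone and bad-tone weeks together, allowing for repeated weeks within a dyad. A t-test on per-dyad proportions stays closest to the present plan; GEE clustered on dyad is an alternative. State that the good-tone share is not a tone effect by itself, because it rises with talking, and is to be read with the bad-tone share and talk frequency. Report mean tone among talkers as descriptive, labelled as conditional on talking.

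The cost is a few derived variables and a sentence in items 4 and 5. No new data are needed. Some detail across the five tone levels is lost in the compared outcomes, and weeks with no answer remain missing, as they do now.
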